6.4.9.6. Patient Global Impression of Change Scale

The PGIC is a validated generic tool for the assessment of overall change in the severity of illness following treatment. Patients will be asked to rate the change in their overall health and well-being since the study start (the time after patient received the first IMP dose) on a 7-point scale as the follows:

- 1 = Much worse
- 2 = Moderately worse
- 3 = Slightly worse
- 4 = Stayed the same
- 5 = A little better
- 6 = Moderately better
- 7 = Much better

Patients will record responses to the PGIC scale in the electronic diary device at home at week 1 (day 7) and in the investigational site tablet at visits 3, 4, and 5.

For analysis purpose, a dichotomous scale of Yes or No will be derived. A favorable change is score of 5-7, which means there is improvement (Yes) with the treatment. If the response is 1-4, it is considered no improvement (No).

The percentage of patients' dichotomous scale of Yes or No rated by PGIC assessments at each visit will be analyzed using a CMH method in a manner analogous to the first secondary endpoint as described in Section [6.3.1](#).

Raw data will be summarized using descriptive statistics for each visit. Missing category will be presented if applicable.

7. MULTIPLE COMPARISONS AND MULTIPLICITY

Hochberg's step-up method will be implemented to test primary and secondary endpoints while controlling the overall type 1 error rate at 0.05.

The treatment comparisons will be for the fremanezumab 900-mg iv loading dose group versus placebo [H_{01}] and the fremanezumab 675-mg sc loading dose group versus placebo [H_{02}]. According to Hochberg step-up method, the rules of multiple comparisons for 2 null hypotheses for the primary endpoint are as follows:

1. If the resulting 2-sided p-values from both comparisons are ≤ 0.05 (reject both null hypotheses), then the next comparison of interest will be interpreted inferentially at the alpha level of 0.05 and statistical significance will be claimed for both active dose groups. Testing of secondary efficacy measures will be continued.
2. If the resulting 2-sided p-value from 1 of comparisons is > 0.05 (fail to reject the null hypothesis) and other resulting 2-sided p-value is ≤ 0.025 ($\frac{\alpha}{2} = 0.025$; reject the null hypothesis), then the result from the comparison with p-value ≤ 0.025 will be interpreted inferentially at the alpha level of 0.05, and statistical significance will be claimed for this active dose group. No further comparisons will be interpreted inferentially.
3. If the resulting 2-sided p-value from both comparisons are > 0.05 (fail to reject both null hypotheses), then no statistical significant will be claimed and no comparisons will be interpreted inferentially.

If the resulting 2-sided p-values from both comparisons for the primary endpoint are ≤ 0.05 (reject both hypotheses; case 1 as described above), testing of secondary efficacy measures will proceed at an error rate of 0.05 in the sequential manner as specified in Section 1.2. The same testing rules as described above will be followed. This process will continue either until all comparisons of interest for secondary endpoints are interpreted inferentially or until the point at which the resulting 2-sided p-value for a comparison of interest is > 0.05 . At the point where a 2-sided p-value > 0.05 , the testing process stops. No further comparisons will be interpreted inferentially.

For the last secondary endpoint (PPSI assessments), only the assessment at week 12 will be included in the multiple comparisons.

8. SAFETY ANALYSIS

8.1. General

The safety analysis set will be used for all safety analyses. Summaries will be presented using descriptive statistics by treatment group and all fremanezumab as actually received unless otherwise stated.

8.2. Duration of Exposure to Study Drug

At the visit 2, each patient will receive a 1-hour iv infusion and 3 sc injections of fremanezumab or placebo. At visits 3 and 4, patients will receive 1 sc injection of fremanezumab or placebo.

Duration of the treatment period (days) for a patient is defined as the number of days a patient is in the double-blind treatment period and calculated as date of EOT visit - first date of the IMP + 1. For patients who are lost to follow-up, the date of EOT visit is defined as the date of last IMP administration + 27. Duration of iv infusion (minutes) will be calculated for the infusion as stop date/time of infusion - start date/time of infusion. Dosing visit interval (days) is defined as the number of days between dosing visit (dose 1 and dose 2; dose 2 and dose 3) and calculated as date of next dosing - date of current dosing.

Duration of the treatment period (days), duration of iv infusion (minutes), dosing visit interval (days), the number of doses received, total number of injections received (placebo or fremanezumab), and reasons for IMP not administrated will be summarized using descriptive statistics. Summary will be presented by treatment group.

IMP administration and accountability data will be listed.

8.3. Adverse Events

Adverse events will be recorded from time informed consent is obtained through the end of study participation.

The following are considered protocol-defined adverse events of special interest to be sent to the sponsor's Global Patient Safety and Pharmacovigilance Department for evaluation: ophthalmic-related adverse events of at least moderate severity, events of possible drug-induced liver injury (aspartate aminotransferase or alanine aminotransferase $\geq 3 \times$ the upper limit of normal [ULN], total bilirubin $\geq 2 \times$ the ULN, or international normalized ratio >1.5), Hy's Law events, or events of anaphylaxis and severe hypersensitivity reactions.

All adverse events will be coded using MedDRA (version 18.1). Each patient will be counted only once in each preferred term or SOC category for the analyses of safety. Summaries will be presented for all adverse events (overall and by severity), adverse events determined by the investigator to be related to test IMP (defined as related or with missing relationship) (overall and by severity), serious adverse events, and adverse events causing withdrawal from the study. Adverse events with the missing flag indicating serious will be excluded from the summary of serious adverse events but included in the summary of non-serious adverse events.

Summaries for injection site and infusion-related adverse events and protocol-defined adverse events of special interest will be presented (overall and by severity).

Listings for deaths, serious adverse events, adverse events leading to discontinuation, injection site and infusion-related adverse events, and protocol-defined adverse events of special interest will be presented. In addition, listings for MedDRA dictionary terms for adverse event descriptions and adverse event preferred terms by patient number and treatment group will be presented.

Spontaneous abortion or an elective abortion due to developmental anomalies will be reported as a serious adverse event (protocol Section 7.2). These serious adverse events will be listed separately if applicable.

Summaries will include treatment-emergent adverse events which are defined as adverse events occurring at or after the first dose of the IMP. The listing will include all adverse events recorded.

Adverse events for patients who did not meet screening criteria will be listed.

8.4. Injection Site Assessments

Injection site assessments will be performed immediately (+10 minute) and 1 hour (± 15 minutes) after receiving each dose of the IMP at visits 2, 3 and 4. The injection site(s) will be assessed for erythema, induration, and ecchymosis. More details are in Section 7.11 of the study protocol.

Injection-site reactions should be recorded as adverse events. Injection-site related adverse events will be summary as indicated in Section 8.3.

8.5. Hypersensitivity/Anaphylaxis

Patients will be assessed for suspected anaphylaxis reaction during and after administration of the IMP (through 1 hour postdose) at visits 2, 3, and 4. Data will be summarized using descriptive statistics.

The number of patients with suspected anaphylaxis reactions and number of suspected anaphylaxis reactions per patient will be summarized using descriptive statistics.

The relative time of suspected event will be calculated as date/time of suspected event - date/time of most current IMP administration and summarized using descriptive statistics. If a patient has more than one suspected anaphylaxis reactions, the earliest time will be used for the calculation.

Data will be listed.

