#### **1.3.1. Known and Potential Benefits and Risks of the Test Investigational Medicinal Product(s)**

Results from Phase 2b clinical studies have demonstrated statistically significant reductions in mean headache hours after 1, 2, and 3 months of sc fremanezumab treatment in patients with chronic migraine and statistically significant reductions in monthly migraine days after 1, 2, and 3 months of fremanezumab treatment in patients with episodic migraine. Results for several secondary/exploratory endpoints also showed fremanezumab to be superior to placebo.

Fremanezumab has generally been well tolerated over the ranges of doses evaluated (single iv infusions at 0.02 to 2000 mg in healthy subjects, multiple iv infusions at 30 to 300 mg in healthy subjects, and multiple sc doses at 225 to 900 mg in healthy subjects and migraine patients). The most common treatment-emergent adverse events across all patients/subjects studied were mild to moderate transient general administration site disorders/reactions. Other commonly reported treatment-emergent adverse events were headache, back pain, and upper respiratory tract infection.

Reports of mild to moderate transient administration site disorders/reactions, including injection site bruising, injection site swelling, administration site pain, injection site pain, injection site pruritus, injection site dermatitis, injection site rash, injection site edema, injection site discomfort, injection site hemorrhage, injection site irritation, injection site mass, and injection site hematoma, have occurred with sc administration. In addition, reports of mild and transient infusion site pain and swelling following iv administration have occurred. Among these events, the following have been identified as adverse drug reactions (identified risks): injection site erythema, administration site pain, injection site pain, injection site pruritus, and injection site dermatitis. None of these identified risks are considered important risks.

Infusion-related reaction and drug hypersensitivity were also identified as adverse drug reactions. To date, 1 subject who received fremanezumab iv had a non-serious infusion-related reaction, and 1 patient who received fremanezumab via the sc route had a non-serious event of drug hypersensitivity. Both events resolved following IMP discontinuation and treatment with diphenhydramine and methylprednisolone. Neither of these identified risks are considered important risks.

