- t Partners/family members will be asked to attend the study visit with the patient or to return to the investigational center within  $\pm 3$  days of the patient's visit if unable to appear at the same time.
- u Responses at week 1 will be recorded in the electronic diary device at home, and responses at all other time points will be entered into the investigational site tablet.
- v Patients will return the wearable sensor if they do not rollover into the long-term safety study (Study TV-48125-CNS-30058) or if they rollover into the long-term safety study but do not wish to continue participating in the wearable sensor substudy.
- w The eC-SSRS Baseline/Screening version will be completed at visit 1, and the eC-SSRS Since Last Visit version will be completed at all other visits, including unscheduled visits. Results from both versions will be entered into the investigational site tablet.
- x Patients randomized to the 900-mg iv loading dose group will receive 900 mg of fremanezumab administered via an approximately 1-hour iv infusion followed by 3 placebo sc injections at visit 2 (week 0) and fremanezumab at 225 mg administered as single sc injections at visits 3 and 4 (weeks 4 and 8, respectively). Patients randomized to the 675 mg sc loading dose group will receive placebo administered via an approximately 1-hour iv infusion followed by fremanezumab at 675 mg administered as 3 sc injections (225 mg/1.5 mL) at visit 2 (week 0) and fremanezumab at 225 mg administered as single sc injections at visits 3 and 4 (weeks 4 and 8, respectively). Patients randomized to the placebo group will receive placebo as an approximately 1-hour iv infusion followed by placebo administered as 3 placebo sc injections at visit 2 (week 0) and placebo as single sc injections at visits 3 and 4 (weeks 4 and 8, respectively).
- y Patients will be assessed for hypersensitivity reactions and anaphylaxis during and after administration of the IMP (through 1 hour postdose).

Clinical Study Protocol with Amendment 02

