#### **Visit 3 (Week 4 [Day 28+3 Days])**

The following predose procedures and assessments will be performed at visit 3:

- Review study compliance.
- Review electronic diary data.
- Perform vital signs measurements (includes systolic and diastolic blood pressure, pulse, and body temperature).
- Inquire about adverse events.
- Inquire about concomitant medications.
- Perform clinical laboratory tests (serum chemistry, hematology, coagulation, and urinalysis).
- Perform urine  $\beta$ -HCG pregnancy test (for women of childbearing potential only).
- Obtain a 4-mL blood sample for pharmacokinetics analysis from either arm.
- Obtain a 5-mL blood sample for ADA analysis.
- Administer the HADS, EQ-5D questionnaire, SF-12, and WPAI questionnaire.

- Each patient’s partner/family member completes the Impact on Partner and Family questionnaire. Partners/family members will be asked to attend the study visit with the patient. Partners/family members will be asked to attend the study visit with the patient or to return to the investigational center within  $\pm 3$  days of the patient’s visit if unable to appear at the same time.
- Complete the PPSI.
- Complete the PGIC scale.
- Complete the eC-SSRS Since Last Visit version.
- Perform wearable sensor device check and compliance check for patients enrolled in the wearable sensor substudy.

In addition, a 6-mL blood sample for pharmacogenomic analysis (DNA) may be obtained at this visit if the sample is not obtained at visit 2 (week 0), unless the patient declines or local regulations prohibit pharmacogenomic testing.

After completing predose assessments, patients will be treated with IMP. Refer to Section 5.1.1.1 for details regarding IMP administration.

The following procedures and assessments will be performed at visit 3 (week 4) after dosing:

- Perform local injection site assessment immediately (+10 minutes) and at 1 hour ( $\pm 15$  min) after completing IMP administration. Additional injection site assessments may be performed based on the severity of any observed injection site reaction. See Section 7.11 for additional details.
- Evaluate for anaphylaxis and hypersensitivity reactions.
- Inquire about postdose adverse events before the patient leaves the study center.

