1.3. Safety Endpoints

The safety endpoints are as follows:

- occurrence of adverse events throughout the study
- clinical laboratory (serum chemistry, hematology, coagulation, and urinalysis) test results at each visit
- vital signs (systolic and diastolic blood pressure, oral temperature, and pulse rate) measurements at each visit. Note: Oxygen saturation will be measured in cases of suspected anaphylaxis and severe hypersensitivity. Respiratory rate will also be measured in these cases but not as a standard vital sign.
- 12-lead electrocardiogram (ECG) findings at screening, baseline, and week 12

- use of concomitant medication during the study
- clinically significant changes in physical examinations, including body weight
- injection site reaction (ie, erythema, induration, and ecchymosis) and injection site pain assessments
- occurrence of hypersensitivity/anaphylaxis reactions
- suicidal ideation and behavior as measured by the electronic Columbia Suicide Severity Rating Scale (eC-SSRS)

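### SAP 8.5 counts only suspected anaphylaxis, so its summary is narrower than the hypersensitivity/anaphylaxis safety endpoint it addresses

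*SAP*

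**What the plan says.** Protocol 2.1 and SAP 1.3 list the same safety endpoint: "occurrence of hypersensitivity/anaphylaxis reactions". Protocol Table 2, in its footnote on the reaction assessment, requires that "Patients will be assessed for hypersensitivity reactions and anaphylaxis during and after administration of the IMP (through 1 hour postdose"), and Appendix B repeats the instruction after dosing at visits 2, 3 and 4 (at visit 3: "Evaluate for anaphylaxis and hypersensitivity reactions").

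SAP 8.5 carries both terms in its heading. Its description of the assessment does not: "Patients will be assessed for suspected anaphylaxis reaction during and after administration of the IMP (through 1 hour postdose"). The counting rule follows the narrower term: "The number of patients with suspected anaphylaxis reactions and number of suspected anaphylaxis reactions per patient will be summarized using descriptive statistics". So does the rule for repeated events: "If a patient has more than one suspected anaphylaxis reactions, the earliest time will be used for the calculation".

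SAP 8.3 includes among the events of special interest "or events of anaphylaxis and severe hypersensitivity reactions". It summarizes that category overall and by severity, and does the same for injection-site and infusion-related events. It also tabulates all adverse events by system organ class and preferred term.

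Protocol 1.3.1 gives the background: "Infusion-related reaction and drug hypersensitivity were also identified as adverse drug reactions". It reports one case of each, both non-serious, and says that neither is considered an important risk.

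**The concern.** An endpoint that names two kinds of reaction is given counting rules for one of them. The reactions left out, hypersensitivity that is neither severe nor suspected anaphylaxis, belong to a class that the protocol already lists as an adverse drug reaction.

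The SAP states in its Introduction that it prevails where it differs from the protocol, so a programmer would follow 8.5 as written. The table produced under a hypersensitivity/anaphylaxis heading would then hold anaphylaxis data only. A reader could take a low or zero count there as the result for the whole endpoint, when the milder reactions sit elsewhere under separate preferred terms with no grouping to bring them together.

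**Working it through.** The plan states no figure to reproduce. The check is a comparison of texts, followed by a rough size.

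**Step 1: definition against derivation.**

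| Source | Scope |
|---|---|
| Protocol 2.1 and SAP 1.3, endpoint | hypersensitivity and anaphylaxis |
| Protocol Table 2 and Appendix B, assessment | hypersensitivity and anaphylaxis |
| SAP 8.5, assessment sentence | suspected anaphylaxis |
| SAP 8.5, patients with events and events per patient | suspected anaphylaxis |
| SAP 8.5, timing rule for repeated events | suspected anaphylaxis |

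The heading of 8.5, a generic sentence on summarizing the data and a loose reference to a suspected event hint at wider scope. No rule in the section counts a hypersensitivity reaction that is not suspected anaphylaxis.

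**Step 2: where each kind of reaction is counted.**

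| Reaction, if recorded as an adverse event | SAP 8.5 | Special-interest summary (8.3) | General tables (8.3) |
|---|---|---|---|
| Suspected anaphylaxis | yes | if recorded as anaphylaxis | yes |
| Severe hypersensitivity, not suspected anaphylaxis | no | yes | yes |
| Non-severe hypersensitivity, not suspected anaphylaxis | no | no | yes |

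Protocol 7.1.7 monitors severe hypersensitivity with the anaphylaxis criteria, so some cases in the second row may in practice be recorded as suspected anaphylaxis. The third row is the clear gap. Some of those reactions may also appear in the infusion-related summary, but only if they happen to be classed that way.

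**Step 3: is the gap filled by a cross-reference?** SAP 8.4 shows how the SAP does this elsewhere: it refers injection-site adverse events explicitly to the summaries in 8.3. SAP 8.5 has no such sentence, and 8.3 defines no hypersensitivity grouping beyond the severe one.

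**Step 4: size.** Inputs:
- 1 drug hypersensitivity case to date (protocol 1.3.1)
- 484 subjects and patients exposed in completed studies (protocol 1.2.2)
- about 100 patients planned per group and two active groups (protocol 3.2), so n = 200

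Assumptions: the case belongs to those 484, and the rate carries over to this trial's regimens.

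- Rate: p = 1/484 = 0.00207, about 0.2%.
- Expected patients: 200 × 0.00207 = 0.41.
- Chance of at least one: 1 − (1 − 0.00207)^200 = 0.34.

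As a sensitivity check, adding the one infusion-related reaction gives 2/484 = 0.00413, 200 × 0.00413 = 0.83 patients and 1 − (1 − 0.00413)^200 = 0.56.

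A rate based on one event is very imprecise. The exact 95% limits for 1/484 are about 0.005% and 1.15%. The upper limit solves (1 − p)^484 + 484p(1 − p)^483 = 0.025; the lower solves 1 − (1 − p)^484 = 0.025. At 0.005% the expected number is 200 × 0.00005 = 0.01 patients; at 1.15% it is 200 × 0.0115 = 2.3.

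**The case against.** The strongest reply is that nothing goes unreported. Any hypersensitivity reaction recorded as an adverse event is tabulated by preferred term and system organ class, by severity and by relationship to the test product, and again if it is serious or leads to withdrawal. Severe cases have their own special-interest summary and listing, and infusion-related events have theirs. This stands. A reader might infer that milder reactions would be missing from the safety report; the documents do not support that.

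It can also be said that SAP 1.3 does not map endpoints to sections, so 8.5 is not declared the sole source. That is true, but 8.5 is the only section under the endpoint's name, and it points nowhere else. SAP 8.4 shows that the authors add a pointer when they intend one.

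Three further points stand:
- Protocol 9.7 specifies no hypersensitivity analysis, so the entry of no changes in SAP Section 17 is not evidence of an undeclared change of analysis.
- The protocol gives diagnostic criteria for anaphylaxis but none for milder hypersensitivity, so a wider count needs a term list that does not yet exist.
- The case report form is not in the documents. The wording of 8.5 may simply match what the assessment form records.

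Safety analysis is descriptive, so no test or type I error depends on this section.

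**Conclusion.** The point holds as a gap in the derivation of one safety endpoint. Applied as written, SAP 8.5 leaves non-severe, non-anaphylactic hypersensitivity out of the count for an endpoint that includes it by name. It does not hold as a gap in safety capture.

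The likely size is small: about 0.4 expected patients among 200, with about a 34% chance of at least one. This rests on a single prior case, on 484 being the right denominator, and on the rate carrying over from healthy subjects and migraine patients. The documents do not say how severe that case was beyond non-serious, so it may not be of the uncounted kind.

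A reader might infer that several patients will almost certainly be left out; the documents give no rate that would support this. Nor do they support tying the concern to the size of the iv loading dose. They do not give the doses of the companion episodic cluster headache study, the one hypersensitivity case followed sc dosing, and single iv doses up to 2000 mg are described as generally well tolerated in healthy subjects. The reason for the change is the mismatch between endpoint and summary, which does not depend on any rate.

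**What to change.** Reword SAP 8.5 to report, by treatment group and for all fremanezumab:

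- (a) the number of patients with any hypersensitivity reaction, whatever its severity, from adverse events coded to a term list fixed before unblinding plus any such reactions recorded at the Table 2 assessments;
- (b) the number with suspected anaphylaxis, kept as now and shown as a subset of (a).

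Give events per patient for both, and time from dose where times are recorded. Make coded adverse events the main source for (a), because the documents do not show whether the assessment form captures non-anaphylactic reactions. The minimum alternative is one sentence in 8.5, on the model of 8.4, naming a prespecified hypersensitivity grouping in 8.3 that supplies the endpoint.

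The cost is a term list to agree, one extra table and possibly a slightly higher reported incidence. No new visit or procedure is needed. The list must be settled before unblinding, since one chosen afterwards would be post hoc.
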